16.32 Definitions and Analyses of Secondary Endpoints (Both Cohorts)

16.321 Survival time is defined as the time from registration to death due to any cause. The distribution of survival time will be estimated using the method of Kaplan-Meier (1958).

16.322 Adverse events: All eligible patients that have initiated treatment will be considered evaluable for assessing adverse event rate(s). The maximum grade for each type of adverse event will be recorded for each patient, and frequency tables will be reviewed to determine patterns. Additionally, the relationship of the adverse event(s) to the study treatment will be taken into consideration.

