3.2 Exclusion Criteria

- 3.21 Patients who have had chemotherapy or radiation \leq 2 weeks of registration.
- 3.22 For Cohort 1 only: Patients with evidence of Intermediate 2 or High risk disease (according to DIPSS, see Appendix VI).
- 3.23 For Cohort 1 only: Patients with a bone marrow biopsy with $<15\%$ cellularity, evidence of collagen fibrosis, osteosclerosis, or blasts $> 10\%$ in peripheral blood or marrow (demonstrating advanced disease).
- 3.24 Patients who have received a prior stem cell transplant
- 3.25 Patients who have received radiation to the spleen within 3 months prior to registration
- 3.26 Patients with intolerance to compounds similar to pegylated interferon alpha-2b.
- 3.27 Patients with evidence of \geq grade 2 peripheral sensory neuropathy.
- 3.28 Any of the following, because this study involves an investigational agent whose genotoxic, mutagenic and teratogenic effects on the developing fetus and newborn are unknown:
 - Pregnant women
 - Nursing women
 - Men or women of childbearing potential who are unwilling to employ adequate contraception
- 3.29a Co-morbid systemic illnesses or other severe concurrent disease which, in the judgment of the investigator, would make the patient inappropriate for entry into this study or interfere significantly with the proper assessment of safety and toxicity of the prescribed regimens.
- 3.29b Immunocompromised patients or patients known to be HIV positive and currently receiving antiretroviral therapy.
- 3.29c Uncontrolled simultaneous illness including, but not limited to, ongoing or active infection, symptomatic congestive heart failure, unstable angina pectoris, cardiac

arrhythmia, history of depression, or psychiatric illness/social situations that would limit compliance with study requirements.

- 3.29d Receiving any other investigational agent which would be considered as a treatment for the primary neoplasm.
- 3.29e History of myocardial infarction \leq 6 months prior to registration, or congestive heart failure requiring use of ongoing maintenance therapy for life-threatening ventricular arrhythmias.
- 3.29f History of significant or major fundoscopic findings including, but not limited to, retinal exudates, hemorrhage, detachment, neovascularization, papilloedema, optic atrophy, micro-aneurysm or macular changes.
- 3.29g Other active malignancy at time of registration. EXCEPTIONS: Non-melanotic skin cancer or carcinoma-in-situ of the cervix.

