6.2 Correlative Research

A mandatory correlative research component is part of this study, the patient will be automatically registered onto this component (see Sections 3.19c and 14.0).

6.3 Documentation of IRB approval must be on file in the Registration Office before an investigator may register any patients.

In addition to submitting initial IRB approval documents, ongoing IRB approval documentation must be on file (no less than annually) at the Registration Office [REDACTED] [REDACTED] If the necessary documentation is not submitted in advance of attempting patient registration, the registration will not be accepted and the patient may not be enrolled in the protocol until the situation is resolved.

When the study has been permanently closed to patient enrollment, submission of annual IRB approvals to the Registration Office is no longer necessary.

6.4 Prior to accepting the registration, registration application will verify the following:

- IRB approval at the registering institution
- Patient eligibility
- Existence of a signed consent form

- Existence of a signed authorization for use and disclosure of protected health information

6.5 At the time of registration, the following will be recorded:

- Patient has/not given permission to store and use his/her sample(s) for future research of Myelofibrosis at Mayo.
- Patient has/not given permission to store and use his/her sample(s) for future research to learn, prevent, or treat other health problems.
- Patient has/not given permission for MCCC to give his/her sample(s) to researchers at other institutions.

6.6 Treatment cannot begin prior to registration and must begin \leq 14 days after registration.

6.7 Pretreatment tests/procedures (see Section 4.0) must be completed within the guidelines specified on the test schedule.

6.8 All required baseline symptoms (see Section 10.51) must be documented and graded.

6.9 Treatment on this protocol must commence at Mayo Clinic Arizona under the supervision of a hematologist or healthcare professional.

6.9a Study drug is available on site.

6.9b Patient questionnaire booklet is available on site; copies are not acceptable for this submission.

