13.0 Treatment/Follow-up Decision at Evaluation of Patient

- 13.1 Patients who are without progression will continue treatment per protocol.
- 13.2 Patients who develop PD while receiving therapy will go to the event-monitoring phase.
- 13.3 Patients who go off protocol treatment for reasons other than PD will go to the event-monitoring phase per Section 18.0.
- 13.4 A patient is deemed *ineligible* if after registration, it is determined that at the time of registration, the patient did not satisfy each and every eligibility criteria for study entry. The patient will go directly to the event-monitoring phase of the study (or off study, if applicable).
 - If the patient received treatment, all data up until the point of confirmation of ineligibility must be submitted. Event monitoring will be required per Section 18.0 of the protocol.
 - If the patient never received treatment, on-study material and the end of active treatment/cancel notification form must be submitted. No further data submission is necessary.
- 13.5 A patient is deemed a *major violation*, if protocol requirements regarding treatment in cycle 1 of the initial therapy are severely violated that evaluability for primary end point is questionable. All data up until the point of confirmation of a major violation must be submitted. The patient will go directly to the event-monitoring phase of the study. Event monitoring will be required per Section 18.0 of the protocol.
- 13.6 A patient is deemed a *cancel* if he/she is removed from the study for any reason before any study treatment is given. On-study material and the End of Active Treatment/Cancel Notification Form must be submitted. No further data submission is necessary.

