16.211 STAGE 1(Cohort 2 only): Enter 12 patients into the study. If 0 successes are observed in the first 12 evaluable patients, we will consider this regimen ineffective in this patient population and terminate this study. If 4 or more successes are observed in the first 12 evaluable patients, we may recommend further testing of this regimen in subsequent studies in this population (a decision to complete the planned accrual specified by the design will be based on availability of budget, assuming no safety concerns). Otherwise, if the number of successes is 1, 2, or 3, we will consider a protocol amendment to expand to Stage 2. In cohort 2, after the first 3 patients are enrolled a recruitment pause will occur as a safety precaution measure. Safety/toxicity data will be analyzed in these 3 patients and a decision to continue the study will be made by the Principal Investigator, statistician and study team. .

16.212 STAGE 2(Cohort 2 only): Enter an additional 23 patients into the study. If 6 or fewer successes are observed in the first 35 evaluable patients, we will consider this regimen ineffective in this patient population. If 7 or more successes are observed in the first 35 evaluable patients, we may recommend further testing of this regimen in subsequent studies in this population.

16.213 Over Accrual: If more than the target number of patients are accrued, the additional patients will not be used to evaluate the stopping rule or used in any decision making process. Analyses involving over accrued patients is discussed in Section 16.34.

16.22 Sample Size: The two-stage study design to be utilized is fully described in Section 16.21. A minimum of 12 and a maximum of 35 evaluable patients will be accrued onto this phase II (Cohort 2 only) study unless undue toxicity is encountered. **We are currently planning to enroll to Stage 1 only.** We anticipate accruing an additional 1 patient to Stage 1 to account for ineligibility, cancellation, major treatment violation, or other reasons. Maximum projected accrual to Stage 1 is therefore **13 patients for cohort 2**. Anticipated enrollment in cohort 1 is expected to be low, therefore a maximum of 6 patients will be

enrolled in cohort 1. Cohort 1 will be analyzed for descriptive purposes only, Total sample size is a maximum of 19 patients in both cohorts for Stage 1.

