Accrual will be temporarily suspended to this study if at any time we observe events considered at least possibly related to study treatment (i.e. an adverse event with attribute specified as “possible”, “probable”, or “definite”) that satisfy the following:

- if 2 or more patients in the first 6 treated patients in either cohort (or 30% after the first 6 treated patients have been accrued) experience a grade 4 or higher non-hematologic adverse event.

We note that we will review grade 4 and 5 adverse events deemed “unrelated” or “unlikely to be related”, to verify their attribution and to monitor the emergence of a previously unrecognized treatment-related adverse event.

16.5 Results Reporting on ClinicalTrials.gov: At study activation, this study will have been registered within the “ClinicalTrials.gov” website. The Primary and Secondary Endpoints (i.e., “Outcome Measures”) along with other required information for this study will be reported on ClinicalTrials.gov. For purposes of timing of the Results Reporting, the initial estimated completion date for the Primary Endpoint of this study is 19 months after the study opens to accrual. The definition of “Primary Endpoint Completion Date” (PECD) for this study is at the time the last patient registered has completed treatment.

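### Adverse event rates count only eligible treated patients, so a patient dosed with P1101 and later found ineligible drops out of them

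*Combined protocol and SAP*

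**What the plan says.** Section 16.322 of the combined protocol and SAP defines who enters the adverse event rates: "All eligible patients that have initiated treatment will be considered evaluable for assessing adverse event rate(s". Two conditions must both be met, eligibility and start of treatment.

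Section 13.4 allows ineligibility to be established after registration, when it emerges that at that time "the patient did not satisfy each and every eligibility criteria for study entry". It provides expressly for the case where dosing has already happened: "If the patient received treatment, all data up until the point of confirmation of ineligibility must be submitted". The patient then goes directly to event monitoring, or off study where applicable.

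Section 16.22 also expects some losses of this kind in cohort 2: "We anticipate accruing an additional 1 patient to Stage 1 to account for ineligibility, cancellation, major treatment violation, or other reasons". Section 2.21 makes the adverse event profile, by cohort, a secondary objective.

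**The concern.** A safety rate is normally read as the experience of everyone exposed to the drug. Here a patient can be exposed, have an event and have the data submitted, and still be outside the reported rate because of an entry criterion that turned out not to be met. I found no section that adds such a patient back or plans an all-treated safety table.

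Cohort membership is itself an eligibility matter. Section 3.22 excludes "For Cohort 1 only: Patients with evidence of Intermediate 2 or High risk disease". A patient registered and treated in cohort 1 who is later found to have been intermediate-2 at registration is therefore ineligible. Section 13.4 gives no route for re-assignment, so that patient would be missing from the rates of both cohorts.

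Nor is eligibility obviously unrelated to safety. Several criteria (3.16 on blood counts and transaminases, 3.29c on depression, 3.29e on cardiac history, 3.29f on fundoscopic findings) concern areas where 15.17 lists harms of this drug class. That fixes no direction of bias, but it is a reason not to filter exposed patients by eligibility. At stake is the completeness of a small descriptive table.

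**Working it through.** **Reading the sections together.** The documents state no adverse event rate or denominator, so there is no figure of the plan to reproduce. The first question is which safety activities carry the eligibility condition.

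| Section | Who is covered | Eligibility condition? |
|---|---|---|
| 16.322, reported rates | eligible and treated | yes |
| 16.42, stopping rule | "if 2 or more patients in the first 6 treated patients in either cohort" | no |
| 16.211, cohort 2 safety pause | "Safety/toxicity data will be analyzed in these 3 patients" | no |
| 16.41, DSMB review | safety data for the trial | no |
| 10.4, serious events | any serious event | no |
| 10.52, routine submission | events by grade and attribution | no |

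The gap is confined to the reported rates. It also means that an event could count towards suspending accrual under 16.42 and yet be absent from the rates under 16.322. A major treatment violation does not remove a patient from 16.322, so only treated ineligible patients are affected.

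**Inputs for size.** From 16.22: cohort 2 Stage 1 maximum 12 + 1 = 13; cohort 1 maximum 6. Assumptions: every enrolled patient is treated, and exactly one in the cohort concerned proves ineligible. The event counts are illustrative.

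**Formula.** Let x of n treated patients have the event, and leave one patient out.

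- If that patient had the event, the shift is (x − 1)/(n − 1) − x/n = −(n − x)/[n(n − 1)]. It is most negative at x = 1, where it equals −1/n.
- If that patient did not, the shift is x/(n − 1) − x/n = x/[n(n − 1)]. It is largest at x = n − 1, where it equals +1/n.

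The limits are therefore ±1/13 = ±7.7 percentage points in cohort 2 and ±1/6 = ±16.7 points in cohort 1.

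**Examples, with exact (Clopper-Pearson) 95% intervals.**

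| Cohort | Omitted patient | All treated | Under 16.322 | Shift (points) |
|---|---|---|---|---|
| 2 | had the event | 2/13 = 15.4% (1.9 to 45.4) | 1/12 = 8.3% (0.2 to 38.5) | −11/156 = −7.1 |
| 2 | no event | 1/13 = 7.7% (0.2 to 36.0) | 1/12 = 8.3% (0.2 to 38.5) | +1/156 = +0.6 |
| 1 | had the only event | 1/6 = 16.7% (0.4 to 64.1) | 0/5 = 0% (0 to 52.2) | −1/6 = −16.7 |
| 1 | no event | 1/6 = 16.7% (0.4 to 64.1) | 1/5 = 20.0% (0.5 to 71.6) | +1/30 = +3.3 |

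The intervals overlap widely in every row. In the third row an observed type of event disappears from the cohort 1 rates altogether. No sample size, significance level or power figure in 16.2 depends on the adverse event population.

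**The case against.** The strongest reply is that this may never happen and would decide nothing. Section 6.4 has eligibility checked at registration: "Prior to accepting the registration, registration application will verify the following", and patient eligibility is on the list that follows. The one-patient allowance in 16.22 covers several kinds of loss together, including cancellations, who by 13.6 are never treated; 13 treated patients in cohort 2 is thus an upper case. No efficacy or stopping rule uses the 16.322 denominator. Nor does 16.322 forbid a listing or footnote for treated ineligible patients. All of this stands, and it keeps the point minor. It does not change who is in the rates.

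The second reply is that including these patients has a price. Section 13.4 requires data only up to confirmation of ineligibility, so a maximum grade taken over shortened follow-up may understate toxicity while the patient adds a full unit to the denominator. Tabulating by registered cohort could also place a patient now known to be intermediate-2 in the early-stage rate, where at most 6 are counted. Both are real drawbacks. A footnote discloses them without removing them, and a separate row for such patients would be another way to present them. Neither drawback is a reason to leave an exposed patient out of the rates.

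**Conclusion.** The concern holds on the plain text. Read with 13.4, 16.322 removes a treated patient later found ineligible from the adverse event rates of a secondary objective, and no other section restores them. The effect is zero if no treated patient proves ineligible, which should be the usual case. If one does, the rate in that cohort moves by at most 1/n in either direction, subject to the assumptions set out above. It is a matter of completeness in a descriptive table; it is neither a demonstrated bias nor a gap in patient protection. Confidence is high in the reading of the text, but the documents do not say how likely such a case is. The change is worth considering mainly because it costs so little, and because settling the population beforehand avoids a choice made once the patient's events are known.

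**What to change.** Replace the population sentence in 16.322 with: *Every patient who receives at least one dose of P1101, whether or not later found ineligible, is evaluable for adverse events and is summarised in the cohort to which the patient was registered.* Keep the eligibility restriction for response in 16.11.

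In the safety table, footnote any treated ineligible patient whose adverse event data stop at confirmation of ineligibility, or whose DIPSS risk group does not match the registered cohort. An eligible-only table can be added as a supplement if wanted.

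The cost is one sentence and a footnote. Section 13.4 already requires these patients' data up to that point, so nothing new is collected. The remaining downside is that such a patient may contribute shorter follow-up or a risk group at odds with the cohort's label; the footnote makes both visible.

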2.2 Secondary

2.21 To evaluate the adverse event profile of P1101 in patients with myelofibrosis by cohort (early vs intermediate-2/high risk)

2.22 To evaluate the tolerability of P1101 in patients with myelofibrosis by cohort (early vs intermediate-2/high risk)

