10.5 Other Required Reporting

10.51 Adverse events to be graded at each evaluation and pretreatment symptoms/conditions to be evaluated at baseline per the CTCAE v4.0 grading unless otherwise stated in the table below:

System/Organ/Class (SOC)	Adverse event/Symptoms	Baseline	Each evaluation
Investigations	White blood cell decreased	X	X
	Neutrophil count decreased	X	X
	Platelet count decreased	X	X
Gastrointestinal Disorders	Diarrhea		X
	# of stools	X	
	Nausea	X	X
	Vomiting	X	X

10.52 Submit via appropriate MCCC Case Report Forms (i.e., paper or electronic, as applicable) the following AEs experienced by a patient and not specified in Section 10.51

10.521 Grade 2 AEs deemed *possibly, probably, or definitely* related to the study treatment or procedure.

10.522 Grade 3 and 4 AEs regardless of attribution to the study treatment or procedure.

10.523 Grade 5 AEs (Deaths)

10.5231 Any death within 30 days of the patient's last study treatment or procedure regardless of attribution to the study treatment or procedure.

10.5232 Any death more than 30 days after the patient's last study treatment or procedure that is felt to be at least possibly treatment related must also be submitted as a Grade 5 AE, with a CTCAE type and attribution assigned.

10.53 Refer to the instructions in the Forms Packet (or electronic data entry screens, as applicable) regarding the submission of late occurring AEs following completion of the Active Monitoring Phase (i.e., compliance with Test Schedule in Section 4.0).

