Appendix V: TRANSFUSION DIARY

Name _____

Patient Medical Record No. _____

Please complete this diary and bring it with you to your next study visit. Write in the date that you received a transfusion, the type of transfusion you received (platelets, red cells, or any other product), and the number of units.

Date of Transfusion	*Type of Product Received (platelets, red cells, other)	Number of Units Received	Pre-Transfusion HGB or Platelet count

*If other, list the type of product

My next scheduled visit is: _____

If you have any questions, please call: _____

Appendix VI: The Dynamic International Prognostic Scoring System (DIPSS) for primary myelofibrosis (PMF)

Each one of these risk factors is assigned 1 adverse point (2 adverse points for hemoglobin lower than 10 g/dL)

- age older than 65 years
- hemoglobin lower than 10 g/dL
- leukocyte count higher than $25 \times 10^9/L$
- circulating blasts $\geq 1\%$
- constitutional symptoms

Risk Group:

Low (0 adverse points)

Intermediate-1 (1 or 2 points)

Intermediate-2 (3 or 4 points)

High (5 or 6 points)

J Clin Oncol 29:392-397. © 2010 by American Society of Clinical Oncology

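### The adverse event tables use the maximum on-study grade without the entry grade, so anemia or fatigue already present at entry can be counted in the P1101 profile

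*Combined protocol and SAP*

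**What the plan says.** Objective 2.21 is "To evaluate the adverse event profile of P1101 in patients with myelofibrosis by cohort". The analysis that serves it is Section 16.322: "The maximum grade for each type of adverse event will be recorded for each patient, and frequency tables will be reviewed to determine patterns". The next sentence adds: "Additionally, the relationship of the adverse event(s) to the study treatment will be taken into consideration". No method is given for that consideration. The section defines neither a treatment-emergent event nor a worsening from entry.

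Section 10.51 sets out "Adverse events to be graded at each evaluation and pretreatment symptoms/conditions to be evaluated at baseline". Its list is white cells, neutrophils, platelets, stool count (diarrhea on study), nausea and vomiting. Section 6.8 makes grading of that list a condition of registration. Anemia and fatigue are not on it.

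Events outside the list reach the case report forms through Section 10.52. Grade 2 events are submitted only if at least possibly related (10.521). For higher grades the rule is "Grade 3 and 4 AEs regardless of attribution to the study treatment or procedure" (10.522).

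Hemoglobin below 10 g/dL is one of the three routes to evaluable disease in Section 3.10. In Appendix VI it is the only factor with a double weight: "2 adverse points for hemoglobin lower than 10 g/dL". Cohort membership is set by the DIPSS category (Section 3.13).

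**The concern.** Anemia and constitutional symptoms belong to myelofibrosis; Section 1.1 calls cytopenias and constitutional symptoms hallmarks of the disease. A patient who enters with a gradable anemia or fatigue and stays the same has no new event, yet a maximum-grade table can show one. The table does not distinguish that patient from one who worsened on P1101.

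The objective is also reported by cohort, and the cohorts are defined by a score that includes hemoglobin. More anemia in Cohort 2 could then reflect who was placed there and be read as poorer tolerability.

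The table has uses beyond description. Section 16.25 brings adverse events into any decision to terminate, Section 16.211 makes further accrual after a Stage 1 success conditional on there being no safety concerns, and Section 16.5 commits the secondary endpoints to public results reporting.

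**Working it through.** The plan states no figure on this point, so there is none to reproduce. The check has three steps.

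**1. Which unchanged entry conditions reach the table**

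| Event at entry, unchanged on study | Submitted? | Source |
|---|---|---|
| Anemia or fatigue, grade 1 | No | 10.52 does not call for it |
| Anemia or fatigue, grade 2, judged unrelated or unlikely | No | 10.521 |
| Anemia or fatigue, grade 2, judged at least possibly related | Yes | 10.521 |
| Anemia or fatigue, grade 3-4 | Yes, any attribution | 10.522 |

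Once submitted, nothing in 16.322 compares the grade with entry. Even the baseline grades that 10.51 does require have no stated use there. Section 11 does measure worsening of anemia, thrombocytopenia and neutropenia from the pre-treatment value, but only to classify response.

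**2. Where DIPSS places entry anemia**

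Inputs from Appendix VI: hemoglobin <10 g/dL scores 2; age, leukocytes, blasts and constitutional symptoms score 1 each. Categories: low 0, intermediate-1 1-2, intermediate-2 3-4, high 5-6. With k of the four one-point factors present there are C(4,k) = 1, 4, 6, 4, 1 profiles for k = 0 to 4.

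- With hemoglobin <10, score = 2 + k. k = 0 gives 1 intermediate-1 profile; k = 1 and 2 give 4 + 6 = 10 intermediate-2; k = 3 and 4 give 4 + 1 = 5 high.
- Without it, score = k. k = 0 gives 1 low profile; k = 1 and 2 give 4 + 6 = 10 intermediate-1; k = 3 and 4 give 4 + 1 = 5 intermediate-2; none is high.

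| Category | Profiles | With hemoglobin <10 g/dL |
|---|---|---|
| High | 5 | 5 |
| Intermediate-2 | 15 | 10 |
| Cohort 2 total | 20 | 15 |
| Low or intermediate-1 (Cohort 1) | 12 | 1 |

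These count combinations of factors. They do not say how many patients have each one.

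**3. Size in the table**

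Cohort 2 has 12 evaluable and at most 13 accrued patients in Stage 1 (Section 16.22). One submitted unchanged event adds 1/12 = 8.3% or 1/13 = 7.7%.

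The share q of Cohort 2 whose unchanged entry anemia is submitted is not given in the documents, so a range is assumed. With no drug effect and a constant grade, the expected count is 12q (exact 95% intervals):

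| Assumed q | Maximum-grade table | Worse than entry |
|---|---|---|
| 0.25 | 3/12 = 25% (5-57%) | 0/12 (upper limit 26%) |
| 0.50 | 6/12 = 50% (21-79%) | 0/12 (26%) |
| 0.75 | 9/12 = 75% (43-95%) | 0/12 (26%) |
| 1.00 | 12/12 = 100% (74-100%) | 0/12 (26%) |

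If q is instead read as the share entering with hemoglobin <10 g/dL, the middle column is an upper bound, because grade 2 anemia judged unrelated is not submitted. The zeros assume that the recorded grade does not move. Ordinary variation between visits will carry some patients across a grade boundary, and a maximum over visits picks those up.

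**The case against.** The best defense is that the plan already has filters and already records entry status. Attribution is assessed on five levels (Section 10.3) and considered in 16.322, and 10.521 keeps unrelated grade 2 events out. The screening column of Section 4.0 includes a CBC, a transfusion assessment, adverse event monitoring and the symptom booklet. Section 18.1 requires a baseline adverse event form, and Section 16.331 analyzes symptom changes. The adverse event table is descriptive, and no test between cohorts is planned.

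Much of this stands, and it rules out several stronger readings:

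- A reader might infer that the disease will inevitably appear as the P1101 profile. With these filters the documents support only that it can.
- A reader might infer that DIPSS builds both anemia and fatigue into Cohort 2. Appendix VI names constitutional symptoms, undefined, and not fatigue. Five of 15 intermediate-2 profiles lack low hemoglobin. Both cohorts are limited to ECOG 0-2, so severe fatigue at entry is not shown to be common.
- A reader might take the listing of anemia and fatigue as expected events in Section 10.31 as a sign of disease origin. Section 10.2 ties expectedness to the drug information in Section 15.0.
- A reader might infer that entry anemia could halt accrual. The rule in Section 16.42 counts only related non-hematologic events of grade 4 or higher.
- A reader might infer that entry anemia goes unrecorded. Its grade can be derived from the screening CBC.

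What the defense does not answer is that attribution concerns cause and does not establish whether an event is new. Section 15.17 lists both anemia and fatigue among reported P1101 events, so a judgment of possible is easy to reach. For grade 3-4 events no attribution filter operates at collection. No section applies an entry grade to the adverse event tables. For fatigue the booklet gives a 0-10 patient rating, which is not a CTCAE grade, and a CTCAE entry grade that was never recorded cannot be recovered later.

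**Conclusion.** The point holds in a limited form. As written, 16.322 can count unchanged entry conditions in the P1101 adverse event profile, chiefly at grade 3-4 and at grade 2 judged at least possibly related. For anemia, this can also distort the display by cohort under objective 2.21. For anemia the gap lies mainly in the analysis rule; for fatigue it lies in data capture as well.

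The size is about 8 percentage points per affected patient in Cohort 2. How many patients are affected is unknown, because the documents give neither the share entering with low hemoglobin nor the CTCAE cut-points that would show which of them are grade 3. The range in the working is illustrative.

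The matter bears on the descriptive safety results and on the judgments made from them. The plan should be changed, since the remedy is cheap.

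**What to change.** In Section 16.322, make the main adverse event table one of events that are new or worse than the patient's entry grade, by cohort, overall and by attribution. Keep the all-event maximum-grade table as a supplement. State that the entry anemia grade is derived from the screening CBC, and say which value is used for a recently transfused patient; Section 11 already has such a convention for response.

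In Section 10.51, add anemia and fatigue, graded at baseline and at each evaluation. Do this early, because a CTCAE entry grade for fatigue has to be recorded prospectively.

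The cost is two rows on the adverse event forms, an extra set of tables and slightly more data entry. There is a side effect: Section 10.52 covers only events not listed in 10.51, so grade 1 and unrelated grade 2 anemia and fatigue would now be recorded too. That raises the counts in the supplementary table, and a footnote there should say so.

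The change removes what was present at entry. It does not separate later disease progression from drug effect, which a single arm cannot do, and the report should say this.
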